Protocol Number: 20220254

National Clinical Trial (NCT) Identified Number: NCT06938230

Principal Investigators: [name], DO & [name]

Grant Title: Maximizing Child Health and Learning Potential: How to Promote A School Culture of Safety in the era of COVID-19

Grant Number: 1OT2HD108111-01

Funded by: National Institutes of Health (NIH) - Eunice Kennedy Shriver National Institute of Child Health and Human Development (NICHD)

Version Date: April 24, 2025

1) Protocol Title

Promoting A School Culture of Safety in the era of COVID-19: Assessing Feasibility and Impact of a Health Education Initiative

2) Objectives*

The primary purpose of this study is to evaluate the feasibility and impact of a COVID-19 health initiative in at-risk urban school settings. This protocol is comprised of 3 components:

- **Part 1A:** Evaluating the feasibility and acceptability of a health education initiative in school health settings.
- **Part 1B:** Assessing COVID-19 knowledge and experience among caregivers of students in at-risk urban school settings post-intervention.
- **Part 1C:** Evaluating the impact of the health education initiative on vaccination rates and other health behaviors 3 months following the intervention.

The second purpose of this study is to compare COVID-19 knowledge, experiences, and health behaviors between participants who received the health initiative and those who did not (controls), through:

- **Part 2A:** Comparing COVID-19 knowledge, experience, and health behaviors of participants in the health education initiative to controls, immediately following the initiative.
- **Part 2B:** Comparing COVID-19 knowledge, experience, and health behaviors of participants in the health education initiative to controls, three months after the initiative.

3) Background*

Covid-19 has infected over 31 million individuals in the United States (CDC, 2021), over 3.54 million of whom were children (AAP, 2021). The pandemic has disproportionately affected racial/ethnic minorities, including children, in terms of infections, hospitalizations, and death (Lopez, Hart, & Katz, 2021; Van Dyke et al., 2021). Other sociodemographic risk factors such as household composition, socioeconomic status, limited English proficiency, housing type, and transportation are also associated with Covid-19 incidence and mortality (Karmakar, Lantz, & Tipireni, 2021).

To mitigate the spread of Covid-19, widespread school closures and shifts to online learning were enacted worldwide. School closures may have disproportionately affected children in low-resourced communities, English learners, and students with disabilities, due to lack of access to remote learning technology and fewer support services outside of school (CDC, 2021). Additionally, children may experience mental distress related to the pandemic and its sequelae, parental stress, risk of abuse and neglect, disruption of routine, and separation from friends (Imran, Zeshan, & Pervaiz, 2020).

Recent data show that there is minimal transmission of Covid-19 between students at schools adhering to safety protocols like masking (Zimmerman et al., 2021). Risks include community transmission, which should be assessed regularly to understand the burden of disease (CDC, 2021). Our own research of positive COVID cases in over 10,000 children in Miami-Dade County found a positivity rate of 11%. When comparing the positivity during the remote-only schooling time period vs. in-person/hybrid time period, the positivity rates dropped from 12.7% to 7.5% supporting the notion that opening schools in person did not increase COVID 19 spread in children. Yet still compared to non-Hispanic white, black Hispanic (aOR=2.53, 95%CI= 1.38-4.66) and white Hispanic (1.96, 1.63-2.37) participants in our sample had higher odds of being COVID-positive.

Though spread of COVID-19 is minimal in the school setting, it is important that vulnerable youth, their families, and school staff feel safe and maintain healthy behaviors, to

avoid absences or quarantine. The school community may therefore benefit from education on the importance of key strategies that stop the spread of Covid-19 – community mitigation and vaccination. The CDC's community mitigation framework includes healthy hygiene, staying home when sick, physical distancing, and use of face coverings (CDC, 2021b). Vaccines have been proven a safe and effective strategy for preventing Covid-19 infection (Thompson et al., 2021). Yet, both are met with mixed reactions by the public. Additionally, there are high rates of vaccine hesitancy among racial/ethnic minority populations, particularly Black Americans (Bunch, 2021; Nguyen et al., 2021).

In a previous study supported by this same funding source, we administered surveys and focus groups to ascertain the knowledge and concerns related to COVID-19 of parents, students (age 14+), and school staff in urban schools in Miami, Florida. Preliminary findings revealed several concerns among stakeholders related to COVID-19 testing and vaccination. Notable barriers identified during the focus groups included questionable information, mixed messages, politicized messages and mistrust. Concerns about the development of the COVID-19 vaccine and potential side effects of the vaccine was highlighted in both qualitative and quantitative data. Resoundingly, transparency about what is known and unknown about the COVID-19 illness and vaccine was emphasized across focus groups. Consideration of cultural beliefs and practices and their relation to health behaviors was also noted. Who delivers health-related information (e.g., healthcare worker, peers) was also noted as important. Preliminary examinations of cross-sectional measures further indicated that perceptions of trust among sources of information differed for students, parents, and school staff. Despite variations in perceived trust, the desire to keep oneself, their family, and their community safe was rated as a motivator for getting vaccinated for most participants.

We propose to incorporate the feedback from the previous study to design a COVID-19 health education initiative that fits the need and culture of the school communities in Miami. We are interested in learning whether attitudes and behaviors about COVID-19 change post intervention. Specially, we predict increased COVID-19 knowledge, increased self-efficacy, and increases in children's vaccination rates.

4) Inclusion and Exclusion Criteria*

Inclusion and exclusion criteria are the same for all components of this protocol.

Inclusion criteria:

- (a) Parents/guardians of students enrolled in: Arch Creek Elementary, Fulford Elementary, Greynolds Park Elementary, Sabal Palm Elementary, North Miami Middle school, JFK Middle School, North Miami Senior High, North Miami Beach High, and Booker T. Washington High.
- (b) Able to read and write in English, Spanish, or Creole at a 5th grade level

Exclusion criteria:

- (a) Does not speak English, Spanish, or Creole.
- (b) Under the age of 18.

5) Procedures Involved*

Arms	Assigned Interventions
Experimental: Health Education Initiative	Behavioral: Health Education Initiative

Participants will receive the health education session for up to 6 months.	Participants will receive a one time 45 minute intervention session. During the session participants will receive information regarding COVID-19 disease process and behavioral effects and had the opportunity to ask questions.
No Intervention: Control Group Participants in this group will not receive any health education and total participation is up to 6 months.	

Intervention Participants

Part 1A (Intervention participants only)

Overview: A health education initiative will be conducted one or more times at each intervention school (i.e., Arch Creek Elementary, Sabal Palm Elementary, JFK Middle, North Miami High, and Booker T. Washington High). This initiative will consist of a panel of health experts, individuals with firsthand experience, and other trusted messengers (e.g., teachers, student champions) presenting on the topic of COVID-19, health safety behaviors, and vaccination. Audience participation and questions will be solicited; content will be adjusted slightly to address each audience's priorities. The initiative may be recorded and made available to the broader school community to expand accessibility. The team will work with representatives from each school to determine the best method for distributing the initiative (e.g., social media). The recording will feature only the images of the panel, to protect the identity of participants.

Consent: To reduce undue burden on participants, we are requesting a waiver of written consent for this portion of the study (see the *Consent Process* section below for more details). Prior to beginning the health education initiative, participants will be provided with information about the study, including study procedures, potential risks/benefits of participation, voluntariness of the study, their right to withdraw, and contact information for the research team, and asked to complete a brief evaluation about the program. Participants will indicate their consent by completing the evaluation form.

Primary Outcome Measures: Participants can choose to complete the following measure immediately following the intervention:

- **Evaluation of acceptability of intervention as measured by Acceptability Questionnaire:**

Participant satisfaction will be assessed via a brief survey evaluating the knowledge gained during the initiative, the value of session, their ability to apply and use information learned, and whether they would recommend the program. Upon completing the survey, participants will be given the option to be contacted in the future to complete an additional survey 3 months later. Demographic information will also be collected. Measure is attached to this protocol.

- Scores range from 1 ("strongly disagree") to 5 ("strongly agree"), with higher scores indicating more knowledge, value, application, or satisfaction.
- Time Frame: up to 6 months
- **Evaluation of confidence in COVID healthcare decision making as measured by COVID Confidence Questionnaire**
 - Scores range from 1 ("strongly disagree") to 5 ("strongly agree"), with higher scores indicating more knowledge, value, application, or satisfaction.
 - Time Frame: up to 6 months
- **Number of caregivers who received COVID-19 vaccine**
 - unit of measure number of caregivers
 - Time Frame: up to 6 months
- **Number of children who received COVID-19 vaccine**
 - unit of measure number of children
 - Time Frame: up to 6 months
- **Health behaviors as measured by Health Behavior Questionnaire**
 - Scores range from 1 ("strongly disagree") to 5 ("strongly agree"), with higher scores indicating greater intent to engage in health behaviors to prevent COVID-19.
 - Time Frame: up to 6 months

Part 1B

Overview: Following completion of the program evaluation, participants will be invited to complete a survey through a secure online data collection method (e.g., REDCap or Qualtrics) or via paper forms that assesses their COVID-19 knowledge and experience. If interested and eligible, participants will be given access to the online survey via a link sent by email, by scanning a QR code, by paper at the event, or may respond to the survey verbally over the phone or in-person, with a study staff member reading aloud questions and recording the participant's responses.

Informed Consent: Informed consent will be obtained electronically via REDCap (detailed below) or on paper, depending on internet availability and participant preference. During the consent process, participants will be given ample time to review study procedures and provided contact information for the research team should they have questions.

Measures: Participants will also be asked to complete the following measure immediately following the intervention:

COVID-19 Knowledge and Experience. COVID-19 knowledge and experience using items from the RADxUP common data elements and the PhenX Toolkit (Hamilton et al., 2011). Data to be collected include basic demographic data, COVID-19 knowledge and attitudes, health risk beliefs, vaccine confidence, COVID-19 related stigma/discrimination, COVID-19 trauma, and COVID-19 anxiety. Measures are attached.

Specific Secondary Outcome Measures:

- **PTSD as measured by the University of California Los Angeles (UCLA Brief COVID-19 Screen for Child/Adolescent Post Traumatic Stress Disorder (PTSD)**

- scores range from 0 to 4, higher scores indicate more symptoms of PTSD
- Time Frame: up to 6 months

- **COVID anxiety as measured by the Coronavirus Anxiety Scale**

- scores range from 0 to 4, higher scores indicate more symptoms of COVID specific anxiety
- Time Frame: up to 6 months

Part 1C

Overview: To assess the impact of the health education initiative on vaccination status and other health behaviors.

Consent: We are requesting a waiver of consent for the first section of Part C which is a few simple questions about the intervention. Informed consent will be obtained electronically via REDCap (detailed below), on paper, or verbally over the phone or in-person, with a study staff member reading aloud questions and recording the participant's responses. During the consent process, participants will be given ample time to review study procedures and provided contact information for the research team should they have questions.

Primary Outcome Measures: Participants will be asked to complete a few questions about the impact of the education session in the last 3 months. Measure is attached.

- **Number of caregivers who received COVID-19 vaccine**
 - unit of measure number of caregivers
 - Time Frame: up to 6 months
- **Number of children who received COVID-19 vaccine**
 - unit of measure number of children
 - Time Frame: up to 6 months
- **Health behaviors as measured by Health Behavior Questionnaire**
 - Scores range from 1 ("strongly disagree") to 5 ("strongly agree"), with higher scores indicating greater intent to engage in health behaviors to prevent COVID-19.
 - Time Frame: up to 6 months

If participants agree they will also be given the opportunity to complete the COVID-19 assessment battery offered in Part B for additional compensation:

COVID-19 Knowledge and Experience. COVID-19 knowledge and experience using items from the RADxUP common data elements and the PhenX Tookit (Hamilton et al., 2011). Data to be collected include basic demographic data, COVID-19 knowledge and attitudes, health risk beliefs, vaccine confidence, COVID-19 related stigma/discrimination, COVID-19 trauma, and COVID-19 anxiety. Measures are attached.

Specific Secondary Outcome Measures:

- **PTSD as measured by the University of California Los Angeles (UCLA) Brief COVID-19 Screen for Child/Adolescent Post Traumatic Stress Disorder (PTSD)**

- scores range from 0 to 4, higher scores indicate more symptoms of PTSD
- Time Frame: up to 6 months
- **COVID anxiety as measured by the Coronavirus Anxiety Scale**
 - scores range from 0 to 4, higher scores indicate more symptoms of COVID specific anxiety
 - Time Frame: up to 6 months

Control Participants

Part 2A

Overview: Control participants will be invited to complete a survey that assesses their COVID-19 knowledge and experience. The survey will be conducted through a secure online data collection method (e.g., REDCap or Qualtrics), paper, or verbally over the phone or in-person, with a study staff member reading aloud questions and recording the participant's responses. If interested and eligible, participants will be given access to the online survey via a link sent by email or by scanning a QR code. If preferred, they will be given the option to complete the survey verbally over the phone or in-person, or to complete it on paper. Control participants may be recruited from any of the study schools (i.e., intervention or control). They must not have participated in the intervention.

Informed Consent: Informed consent will be obtained electronically via REDCap (detailed below) or via paper forms. During the consent process, participants will be given ample time to review study procedures and provided contact information for the research team should they have questions.

Primary Outcome Measures: Participants will complete the following measures:

- **Number of caregivers who received COVID-19 vaccine**
 - unit of measure number of caregivers
 - Time Frame: up to 6 months
- **Number of children who received COVID-19 vaccine**
 - unit of measure number of children
 - Time Frame: up to 6 months
- **Health behaviors as measured by Health Behavior Questionnaire**
 - Scores range from 1 ("strongly disagree") to 5 ("strongly agree"), with higher scores indicating greater intent to engage in health behaviors to prevent COVID-19.
 - Time Frame: up to 6 months
- **COVID-19 Knowledge and Experience.** COVID-19 knowledge and experience using items from the RADxUP common data elements and the PhenX Toolkit (Hamilton et

al., 2011). Data to be collected include basic demographic data, COVID-19 knowledge and attitudes, health risk beliefs, vaccine confidence, COVID-19 related stigma/discrimination, COVID-19 trauma, and COVID-19 anxiety. Measures are attached.

Specific Secondary Outcome Measures:

- **PTSD as measured by the University of California Los Angeles (UCLA) Brief COVID-19 Screen for Child/Adolescent Post Traumatic Stress Disorder (PTSD)**
 - scores range from 0 to 4, higher scores indicate more symptoms of PTSD
 - Time Frame: up to 6 months
- **COVID anxiety as measured by the Coronavirus Anxiety Scale**
 - scores range from 0 to 4, higher scores indicate more symptoms of COVID specific anxiety
 - Time Frame: up to 6 months
-

Part 2B

Overview: Control participants will be invited to complete a follow-up survey that assesses their COVID-19 knowledge and experience approximately three months following the initial survey. The survey will be conducted through a secure online data collection method (e.g., REDCap or Qualtrics), on paper, or verbally over the phone or in-person, with a study staff member reading aloud questions and recording the participants' responses. If interested and eligible, participants will be given access to the online survey via a link sent by email, by scanning a QR code. If preferred, they will be given the option to complete the survey verbally over the phone or in-person, or to complete it on paper.

Informed Consent: Informed consent will be obtained electronically via REDCap (detailed below) or on paper. During the consent process, participants will be given ample time to review study procedures and provided contact information for the research team should they have questions.

Primary Outcome Measures: Participants will complete the following measures:

- **Number of caregivers who received COVID-19 vaccine**
 - unit of measure number of caregivers
 - Time Frame: up to 6 months
- **Number of children who received COVID-19 vaccine**
 - unit of measure number of children
 - Time Frame: up to 6 months
- **Health behaviors as measured by Health Behavior Questionnaire**
 - Scores range from 1 ("strongly disagree") to 5 ("strongly agree"), with higher scores indicating greater intent to engage in health behaviors to prevent COVID-19.
 - Time Frame: up to 6 months

- **COVID-19 Knowledge and Experience.** COVID-19 knowledge and experience using items from the RADxUP common data elements and the PhenX Toolkit (Hamilton et al., 2011). Data to be collected include basic demographic data, COVID-19 knowledge and attitudes, health risk beliefs, vaccine confidence, COVID-19 related stigma/discrimination, COVID-19 trauma, and COVID-19 anxiety. Measures are attached.

Specific Secondary Outcome Measures:

- **PTSD as measured by the University of California Los Angeles (UCLA) Brief COVID-19 Screen for Child/Adolescent Post Traumatic Stress Disorder (PTSD)**
 - scores range from 0 to 4, higher scores indicate more symptoms of PTSD
 - Time Frame: up to 6 months
- **COVID anxiety as measured by the Coronavirus Anxiety Scale**
 - scores range from 0 to 4, higher scores indicate more symptoms of COVID specific anxiety
 - Time Frame: up to 6 months

Compensation

Participants and champions will be issued a Greenphire ClinCard, a reloadable debit card that can be used for studies at the University of Miami. Funds will be loaded on the card according to the payment schedule. The study staff will provide information about how the card works. The company administering the card, Greenphire, requires name, address and date of birth entered online for payment; mobile phone number and/or email address are optional for study related communications. This information will only be used for payment and communication purposes and will not be given to another company or linked to any of the study data. If participants are hesitant to enroll in the study due to requirements for payment with ClinCard, they may be offered a gift card as an alternative.

6) Data and Specimen Banking*

N/A

7) Data Management*

Part 1A: Evaluating the feasibility and acceptability of a health education initiative in school health settings. Post-attendance surveys will be summarized and described by school.

Part 1B: Assessing COVID-19 knowledge and experience among caregivers of students in at-risk urban school settings post-intervention.

Part 1C: Evaluating the impact of the health education initiative on vaccination rates and other health behaviors 3 months following the intervention. Three month post surveys will be summarized and described by school. Assessing COVID-19 knowledge and experience among caregivers of students in at-risk urban school settings 3 months post-intervention.

Part 2A & 2B: Mixed models will be used to examine change in knowledge over time (repeated measure) among participants who have participated in the education session, compared to those who haven't. Likewise, vaccine confidence will be analyzed with a mixed

model to examine change over time, compared to those who did not participate in the education session.

8) Risks to Subjects*

The potential risks in this study are minimal. It is possible some subjects may experience discomfort while responding to questions about COVID-19. However, we incorporated stakeholder feedback on most acceptable methods (i.e., culturally sensitive, addressing their concerns) to discuss COVID-19 testing, diagnosis, and vaccination with participants, to minimize discomfort.

9) Potential Benefits to Subjects*

Participants may gain knowledge about how to maintain health and safety during the era of COVID-19. However, some participants may experience no direct benefit.

10) Vulnerable Populations*

N/A

11) Setting

This study will take place at 9 Miami Dade County Public Schools served by the UM School Health Initiative:

- Intervention schools: Arch Creek Elementary, Sabal Palm Elementary, JFK Middle, North Miami High, and Booker T. Washington High.
- Control schools: Fulford Elementary, Greynolds Park Elementary, North Miami Middle school, and North Miami Beach High or those who did not participate in the intervention at “intervention schools”: Arch Creek Elementary, Sabal Palm Elementary, JFK Middle, North Miami High, and Booker T. Washington High.

12) Resources Available

Our research staff consists of personnel familiar with the protocol. Members of the research team have experience in patient outreach and follow up, conduct of clinical research, statistical analysis and methodology. Additionally, students could seek comprehensive medical services delivered by the School Health Initiative.

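### The recorded session may be released to the school community before control follow-up ends, with no stated rule for controls who watch it

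*Protocol*

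**What the plan says.** The arms table in Protocol Section 5 describes the control condition: "Participants in this group will not receive any health education and total participation is up to 6 months".

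The Part 1A Overview in the same section covers the recording: "The initiative may be recorded and made available to the broader school community to expand accessibility". The team is to work with each school's representatives "to determine the best method for distributing the initiative (e.g., social media" being the example given. The one safeguard stated for the recording is that only the panel is shown, which protects attendees' identity.

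The Part 2A Overview sets the source of controls: "Control participants may be recruited from any of the study schools (i.e., intervention or control). They must not have participated in the intervention". Section 11 (Setting) and Section 14 (Recruitment Methods, Part 2A) repeat this in similar terms. Controls are surveyed again "approximately three months following the initial survey" (Part 2B Overview).

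Section 2 (Objectives) makes the comparison with controls the study's second purpose, at each of the two surveys. For the later one the aim is: "Comparing COVID-19 knowledge, experience, and health behaviors of participants in the health education initiative to controls, three months after the initiative". Section 7 (Data Management) adds mixed models for change over time in knowledge and in vaccine confidence, by group.

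**The concern.** At an intervention school, the people a recording is meant to reach include parents who did not attend. Those same parents may be enrolled as controls. If the plan is followed as written, part of the control group may therefore be given the content that the arms table says controls will not get.

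Parts 2A and 2B are the only comparison with controls. Controls who have watched the recording would be expected to move towards the intervention group, so the comparison would understate any benefit of the session. If exposure is not recorded, no later analysis can recover it. Who counts as a control, and when study material is released, are matters of design and conduct that the protocol fixes, so they are not details to leave to an analysis plan.

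**Working it through.** The protocol states no figure on this point, so the first check is a comparison of its provisions.

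- **Control condition** (Section 5, arms table): no health education, with participation of up to 6 months.
- **Release of the recording** (Section 5, Part 1A): optional. An audience is named and the channel is agreed with each school. No earliest date is given and no link is made to the control surveys.
- **Source of controls** (Section 5, Part 2A; Sections 11 and 14): any of the nine schools, including the five intervention schools, provided the parent did not participate.
- **Status of a viewer**: not stated. The arms table describes a single 45-minute session with a chance to ask questions, which a viewer would not have attended. The common eligibility criteria in Section 4 do not mention the recording.
- **Detection**: the listed control survey content begins "Data to be collected include basic demographic data, COVID-19 knowledge and attitudes, health risk beliefs, vaccine confidence" and continues with stigma, trauma and anxiety. Vaccination and health behaviours are listed separately. Exposure to a recording is not named in either list. The forms themselves are attached to the protocol but not shown.

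Together these provisions permit exposure of controls at any time up to the end of Part 2B, and the text shown gives no means of identifying it.

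The second check is the form the bias would take. Let *d* be the true difference between groups at a survey, *p* the share of all controls who have watched before that survey, and *r* the recording's effect as a fraction of the session's effect. The protocol gives none of these; every value of *p* and *r* below is assumed.

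Observed difference at a survey = *d*(1 − *p·r*), so the proportional shrinkage is *p·r*:

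- *p* = 0.05, *r* = 0.5: 0.05 × 0.5 = 0.025, or 2.5%
- *p* = 0.10, *r* = 0.5: 0.10 × 0.5 = 0.05, or 5%
- *p* = 0.10, *r* = 1: 0.10 × 1 = 0.10, or 10%
- *p* = 0.30, *r* = 1: 0.30 × 1 = 0.30, or 30% (a deliberately high case)
- no release before 2B ends: *p* = 0, so 0%

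Timing decides which comparison is affected:

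- **Viewed before 2A, gain the same at both surveys.** The control mean is raised by *p·r·d* at both. Each survey's difference falls by *p·r·d*, and the contrast in change moves by −*p·r·d* + *p·r·d* = 0.
- **First viewed between 2A and 2B.** The 2A difference is untouched. The 2B difference falls by *p·r·d*, and so does the contrast in change. With *p* = 0.10 and *r* = 0.5, both fall by 0.05*d*, where *d* is the difference at 2B.

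**The case against.** Several points on the other side have force.

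**Definitions.** A reader might infer that the protocol defines controls in two conflicting ways, once as those who did not receive the initiative (Objectives) and elsewhere as those who did not participate. The documents do not support that. The Objectives use both terms for the same group, and Part 1A describes sharing the recording as a way of distributing the initiative. On that wording a viewer has received it and is not a control. What remains is that the status of a viewer is not stated.

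**Audience.** It would be too strong to say that release is unlimited. An audience is named, and the paragraph concerns the five intervention schools. Spread to the four control schools is possible but is not the stated aim.

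**Detection.** A reader might infer that exposure is certain to go unrecorded. The attached forms could contain such a question. Part 2B also limits survey access to eligible people, so eligibility may be checked again at follow-up. The content of that check is not given, so it does not settle the matter.

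**Size.** Release is optional and every magnitude is assumed. This objection stands in full. It limits how large the problem can be said to be, but it does not remove the gap.

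**Conclusion.** The concern holds as a conditional one. The protocol permits a release that would breach its own control condition while control surveys are still running, and the text shown has no provision that prevents or detects this. Release before 2A can dilute the difference at both surveys. Release between 2A and 2B can affect only 2B and the contrast in change.

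The size is unknown. It is zero if nothing is released before the last 2B survey. Under the assumed values it is 2.5% to 10% of the difference at a survey, and 30% in the high case. This rests on viewers gaining something from the recording and on viewers being counted as controls.

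A reader might go further and infer that the control group was contaminated or that the comparison is invalid. The documents do not show that any recording was made or released, so they do not support that inference.

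**What to change.** 1. Hold release of any recording until the last Part 2B survey is complete.
2. State once, and apply in Sections 2, 5, 11 and 14, that watching the recording counts as receiving the initiative.
3. Ask controls at 2A and again at 2B whether they have watched a recording of the session.
4. Do not simply drop viewers. They chose to watch, so removing them from a non-randomised control group takes out parents who may be more interested in the topic and can introduce selection bias. Flag them, and report the 2A and 2B comparisons with and without them.
5. If data are already collected, state whether a recording was released and, if so, when. If none was released before 2B ended, the point is closed.

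The cost is one survey item asked twice, one definition and one release date. Wider access to the recording is delayed until control follow-up ends, about three months after the last control's first survey.
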